#### 4. STUDY OBJECTIVES AND PURPOSE

The primary objectives of this study are to investigate the effectiveness of IMM-101 combined with nivolumab in controlling advanced melanoma and to assess and describe the safety profile of the combination after a maximum of 18 months treatment. The safety and efficacy of the combination will be assessed in patients who are either previously untreated (cohort A), or whose disease has progressed during PD-1 blockade (cohort B) and compared with published data on the efficacy and adverse event profile of nivolumab alone.

## 4.1 PRIMARY OBJECTIVES

- To evaluate Overall Response Rate (ORR) after a maximum of 18 months treatment in patients with advanced melanoma receiving IMM-101 + nivolumab. ORR in both previously untreated patients (cohort A) and in patients whose disease has progressed during PD-1 blockade (cohort B) will be evaluated using RECIST 1.1. ORR will also be assessed for subgroups based on PD-L1 status (positive or negative/undetermined) in cohort A patients.
- To evaluate the safety and tolerability of the combination of IMM-101 + nivolumab in patients with advanced melanoma by examining the profile of adverse events experienced.

## 4.2 SECONDARY OBJECTIVES

- To evaluate Progression-free Survival (PFS) after a maximum of 18 months treatment in patients with advanced melanoma receiving IMM-101 + nivolumab for both cohort A and cohort B, assessed by RECIST 1.1
- To evaluate Overall Survival (OS) and OS at 1 year in patients with advanced melanoma for both cohort A and cohort B.
- To evaluate changes in laboratory parameters.
- To evaluate local tolerability (i.e. injection site reactions).

## 4.3 EXPLORATORY OBJECTIVES

- To evaluate the ORR in patients with advanced melanoma receiving IMM-101 + nivolumab using irRC for both cohort A and cohort B.
- To evaluate the Duration of Response and Time to Response in patients with advanced melanoma receiving IMM-101 + nivolumab for both cohort A and cohort B, assessed by RECIST 1.1.
- To evaluate Disease Control for patients in cohort B of the study only, defined as those patients with a response or stable disease based on RECIST 1.1 during treatment with IMM-101 + nivolumab. To be assessed from response data at Week 14 and at 8 weekly intervals thereafter.
- To evaluate BOR for patients in cohort B to include any responses obtained following a change in therapy from IMM-101 + nivolumab to IMM-101 + ipilimumab.
- To evaluate the safety and tolerability of the combination of IMM-101 + ipilimumab in patients with advanced melanoma by examining the profile of adverse events experienced for any patients in cohort B of the study who took IMM-101 + ipilimumab as subsequent treatment.
- Monitoring of selected markers of tumour burden and immunological status in patients receiving IMM-101 (to be reported separately to other endpoints).

#### 5. STUDY DESIGN AND ENDPOINTS

## 5.1 STUDY DESIGN

IMM-101-015 is an open-label Phase 2a study to investigate the safety and efficacy of IMM-101 in combination with checkpoint inhibitors in patients with advanced unresectable Stage III or Stage IV metastatic melanoma who are either previously untreated (i.e. no prior systemic anticancer therapy for unresectable or metastatic melanoma; cohort A), or whose disease has progressed during PD-1 blockade (cohort B).

Patients suitable for enrolment to cohort B are currently receiving, or have previously received, treatment with an anti-PD-1 therapy (monotherapy or in combination) for advanced melanoma and have progressive disease by RECIST 1.1 after at least 3 doses of anti-PD-1 given as monotherapy or at least 2 doses of anti-PD-1 given in combination regimes, and have not received any therapy since, for advanced melanoma. The last dose of anti-PD-1 therapy must have been received no more than 12 weeks prior to the start of Screening but more than 6 weeks prior to first IMM-101 administration. For all patients in cohort B, progression must have occurred during the PD-1 targeted treatment and the investigator must have deemed it appropriate to continue/start treatment with nivolumab beyond disease progression.

Treatment for patients in both cohorts is continued until disease progression as assessed by RECIST 1.1 subject to the qualifications below, unacceptable side-effects, the Investigator's decision to discontinue treatment, withdrawal of patient consent or 18 months of study treatment, whichever is the sooner. Patients with a complete response maintained over 2 scans should continue treatment unless the investigator considered this is not in the patient's best interest.

Patients in cohorts A and B who have documented disease progression (RECIST 1.1) during the study may continue treatment with IMM-101 + nivolumab on study if they have a clinical benefit and no decline in performance status, no clinically relevant adverse effects with the study treatment as determined by the investigator, and are not deemed to require alternative treatment.

Patients in cohort B who fail to respond to treatment with IMM-101 + nivolumab i.e., they have either documented progression by RECIST 1.1, or clinical progression (but without meeting the RECIST 1.1 rules for progressive disease), and, in both cases have no prior recorded response, have the option to change treatment on study to ipilimumab + IMM-101 if the Investigator considers this in the patient's best interest and the patient has not previously received ipilimumab off study (monotherapy or in combination). This treatment may continue until the maximum 4 doses of ipilimumab have been received or stop sooner due to unacceptable side-effects, the Investigator's decision to discontinue treatment, withdrawal of patient consent or 18 months of study treatment, whichever is the sooner. Patients in cohort B who receive all 4 doses of ipilimumab should remain on study after this time and follow the protocol assessments. They may continue to receive IMM-101 during this period until unacceptable side-effects, the Investigator's decision to discontinue treatment, withdrawal of patient consent or 18 months of IMM-101 treatment, whichever is the sooner.

All patients will be followed up for assessment of safety, response to treatment (via scheduled computerised tomography [CT] or magnetic resonance imaging [MRI scans]) and survival, according to the Study Schedule of Assessments with all patients allowed the opportunity of 18 months of treatment on study. The first scheduled post-baseline scan is at week 12 for patients in cohort A and at week 6 for those in cohort B. Subsequent scans are every 8 weeks with unscheduled scans allowed if clinically indicated, for example to confirm progression. At

Page 31 of 98

the discretion of the Investigator, the frequency of scans may be increased to every 12 weeks for patients who continue on study beyond week 52.

Reviews of all available safety data, to include AEs, biochemistry and haematology and injection site reactions, will take place by the Sponsor and Investigator every 6 months throughout the study. Any signals identified that are believed to impact on patient safety may result in termination of the study.

This Phase 2a open-label study will consist of two phases:

## 1. Screening and Enrolment

Patients who provide informed consent will participate in a screening period of up to a maximum of 21 days to establish eligibility. Once eligibility is confirmed a full disease and treatment history will be taken.

Given the need in this study to relate efficacy to PD-L1 status for patients in cohort A, a tumour sample from an unresectable or metastatic site of disease must be provided that is adequate for PD-L1 assessment prior to enrolment. The tumour sample will be collected during Screening for all patients in cohort A for PD-L1 expression testing unless archived tissue obtained in the preceding 3 months is available. Patients will be eligible to participate regardless of the level of PD-L1 expression. Patients with an inadequate archived sample may obtain a new biopsy and patients with an inadequate newly obtained biopsy may undergo re-biopsy on a further single occasion at the discretion of the Investigator.

#### 2. Treatment Phase

All patients who are confirmed as eligible to participate in the study, and, for female participants who are not surgically sterilised or post-menopausal, have a negative pregnancy test confirmed within 72 hours of first dosing with IMM-101, will enter the Treatment Phase of the study. All patients in both cohorts of the study will receive one 1.0 mg (0.1 mL) dose of IMM-101 every 2 weeks for the first 3 doses followed by a rest period of 4 weeks, then every 2 weeks for the next 3 doses, and thereafter every 4 weeks.

Nivolumab is given every 2 or 4 weeks (dependent on Investigator choice of dosing regimen) to patients in both cohorts of the study.

In instances when nivolumab and IMM-101 are given on the same day, IMM-101 will be administered first (see Section 7.6.1).

If used on study for patients in cohort B, ipilimumab is administered every 3 weeks to a maximum of 4 doses. In instances when ipilimumab and IMM-101 are given on the same day, IMM-101 will be administered first (see Section 7.6.2).

At the discretion of the Investigator the dose of IMM-101 may be adjusted and dosing of IMM-101, nivolumab or ipilimumab delayed according to local skin reactions to IMM-101 and toxicities to all study drugs as detailed in section 7.2.1.

The Treatment Phase will continue for up to the Week 78 visit unless such therapy is contraindicated, the patient does not wish to continue, or the study is terminated by the Sponsor.

Patients will be assessed for response via scheduled scans with the first post-baseline scan at week 12 for patients in cohort A and at week 6 for those in cohort B. Subsequent scans are every 8 weeks with unscheduled scans allowed if clinically indicated, for example to confirm progression. At the discretion of the Investigator, the frequency of

Page 32 of 98

scans may be increased to every 12 weeks for patients who continue on study beyond week 52.

Patients may choose to withdraw from the study at any time and for any reason. Full details of reasons for discontinuation are in section 6.3.

Patients who discontinue study treatment or complete the study should, where possible, attend an end of study visit within 28±7 days after the final dose of IMM-101 when all previously unresolved adverse events will also be followed up. If an end of study visit is not possible any unresolved adverse events and update on concomitant medications should be followed up by other means of contact (e.g. telephone; Section 9.5).

Patients completing or withdrawing from the study will be followed up for survival information until database lock. Any patients who discontinue study treatment for reasons other than progression, and for whom no further treatment is deemed appropriate or desired, should remain on study and have scheduled scans until documented progression.

## 5.2 ENDPOINTS

## **5.2.1** Primary Endpoints

This study has two primary endpoints to measure the two primary objectives of evaluating the safety and the efficacy of the IMM-101 + nivolumab treatment combination.

Safety and Tolerability is measured by:

Adverse events, graded and recorded throughout the study according to NCICTCAE, version 4.03. The incidence, frequency and severity of adverse events, serious adverse events, treatment-related adverse events and immune-related adverse events (as listed in the SmPC for nivolumab) during treatment with IMM-101 + nivolumab will be assessed.

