Safety and Tolerability Endpoints:	
 
The primary safety endpoint is:
 
Incidence, frequency and severity of AEs, SAEs, treatment related AEs, immune-related AEs, Grade 3 and above AEs and AEs leading to IMM-101 discontinuation or study withdrawal experienced during treatment with IMM-101 + nivolumab for both cohorts
 
Secondary safety endpoints are:
 
Incidence and frequency of laboratory parameter abnormalities
 
Change from baseline values in laboratory parameter values
 
Incidence and frequency of local injection site reactions.
 
An exploratory safety endpoint is:
 
For any patients in cohort B of the study who took IMM-101 + ipilimumab as subsequent treatment, the incidence, frequency and severity of AEs, SAEs, treatment related AEs, and immune-related AEs from the start of treatment with ipilimumab.
 

Efficacy Endpoints:	
 
The primary efficacy endpoint is:
 
Overall Response Rate (ORR) calculated from the BOR of patients as assessed by RECIST 1.1. ORR will be assessed at the end of study or when all patients have withdrawn, if this is sooner. For cohort B,
 

	ORR will apply to BOR from tumour assessments during IMM-101 + nivolumab treatment only. ORR and BOR will also be assessed for

Page 20 of 98

subgroups based on PD-L1 status (positive or negative/undetermined) in cohort A patients.

The secondary efficacy endpoints of this study are:

- Progression-free survival (PFS) assessed by RECIST 1.1 after a maximum of 18 months treatment in patients receiving IMM-101 + nivolumab.
- Overall survival (OS) and OS at 1 year, for both cohort A and cohort B. The median OS (if applicable) and OS rate at 12 months will be estimated.

Exploratory efficacy endpoints are:

- ORR using irRC in patients in both cohort A and cohort B receiving IMM-101 + nivolumab.
- Duration of Response and Time to Response for both cohort A and cohort B receiving IMM-101 + nivolumab and assessed by RECIST 1 1
- Disease Control, for patients in cohort B of the study only and defined as those patients with a response or stable disease based on RECIST 1.1., assessed at each scan assessment point from Week 14 onwards.
- BOR for cohort B to include any responses obtained following a change in therapy from IMM-101 + nivolumab to IMM-101 + ipilimumab.
- Immunological markers from blood and biopsy samples (to be reported separately to other endpoints).

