# 7.3 PERMANENT DISCONTINUATION OF STUDY TREATMENT FOR PATIENTS

The prescribing information for nivolumab and for ipilimumab should be referred to for reasons for permanently discontinuing these medications. When treatment discontinuation is indicated for nivolumab or ipilimumab based on adverse events, IMM-101 should also be discontinued. In the event of any immune-mediated adverse reactions of ≥Grade 3 (severe), IMM-101 and nivolumab (or ipilimumab when used for cohort B) should be withdrawn, either until resolution of the event or permanently, at the discretion of the investigator.

Permanent discontinuation for a patient should be considered for any severe or life-threatening adverse reactions, with the final decision on whether to stop treatment made after discussion with the Sponsor.

A dosing delay due to an adverse event failing to resolve or improve to ≤Grade 1 within 12 weeks after last administration of study drug, may result in discontinuation of a patient from study therapy, at the Investigator's discretion and after discussion with the Sponsor. Two dosing delays due to the same toxicity are permitted on study but a third occurrence of the same toxicity which would require dosing delay, will result in permanent discontinuation of the patient from the study. Patients discontinuing the study will be followed up as in Section 6.4.

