#### 9. ASSESSMENT OF SAFETY AND TOLERABILITY

# 9.1 SAFETY AND TOLERABILITY PARAMETERS

One of the primary objectives of this study is to describe the safety profile of IMM-101 combined with nivolumab by assessing the incidence and frequency of adverse events, serious adverse events, treatment-related adverse events and immune-related adverse events (as listed in the SmPC for nivolumab) for the combination of IMM-101 with nivolumab. For cohort A, the final analyses are at the end of the study or when all patients in this cohort have withdrawn if this is sooner but an additional interim safety data review will be performed after all patients in this cohort have had the opportunity for 1 year on study. For cohort B, the final analyses are at the end of study or when all patients in this cohort have withdrawn if this is sooner with an additional interim safety data review when all patients in this cohort have had the opportunity for 6 months on study.

An additional exploratory objective, for any patients in cohort B of the study who took IMM-101 + ipilimumab as subsequent treatment, is the incidence and frequency of adverse events, serious adverse events, treatment-related adverse events and immune-related adverse events (as listed in the SmPC for ipilimumab) following commencement of treatment with the combination of IMM-101 with ipilimumab assessed when all patients have had the opportunity for 6 months on study and again at the end of study.

In addition, reviews of all available safety data, to include AEs, biochemistry and haematology, and injection site reactions, will take place by the Sponsor and Investigator, every 6 months throughout the study, with a particular focus on immune-related AEs. Any signals identified that are believed to impact on patient safety may result in termination of the study.

The combined overall safety profile for IMM-101 including the data obtained from this study will be included in the DSUR annual submission in line with the IBD.

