### 11.1.3 Safety and Tolerability Endpoints

The primary safety endpoints include the following:

• Incidence, frequency and severity of AEs, Serious AEs, treatment-related AEs (related to IMM-101 and/or nivolumab/ipilimumab (as applicable), immune-related AEs (as listed in the SmPC for nivolumab), Grade 3 and above AEs and AEs leading to IMM-101 discontinuation or study withdrawal throughout the study.

The secondary safety endpoints include the following:

- Incidence and frequency of laboratory parameter abnormalities
- Change from baseline values in laboratory parameter values
- Incidence and frequency of local injection site reactions.

Page 77 of 98

Exploratory safety endpoints include the following:

• For the subgroup of patients in cohort B who receive IMM-101 + ipilimumab as subsequent treatment: The incidence, frequency and severity of adverse events, serious adverse events, treatment-related adverse events and immune-related adverse events (as listed in the SmPC for ipilimumab) experienced following the start of ipilimumab treatment up to the end of the study.

Treatment-emergent AEs (TEAEs) are defined as AEs occurring after the first dose of IMM-101. Only TEAEs will be presented in summary tables and all AEs (i.e., TEAEs and non-TEAEs) will be listed by patient within cohort.

TEAEs will be summarised by MedDRA system organ class and preferred term using standard incidence and frequency tables. The incidence of TEAEs will be presented as the proportion of patients with at least one AE by system organ class and preferred term and frequency of TEAEs will be calculated as the number of events by system organ class and preferred term.

Treatment-related AEs are defined as AEs which are related to study treatment (IMM-101 and/or nivolumab, and/or ipilimumab if after ipilimumab dosing in cohort B). Related AEs will be those assigned by the investigator as definitely, probably or possibly related to study treatment or with an unknown relationship. Relatedness will be assessed to each of IMM-101, nivolumab and ipilimumab separately as well as for the combined treatment combination. The incidence and frequency of treatment-related AEs, SAEs, and immune-related AEs will be presented, as for all TEAEs.

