2.2 Study Endpoints

2.2.1 Primary Endpoints

The primary efficacy endpoint of the study is the ORR calculated from the BOR of patients as assessed by RECIST 1.1. ORR will be assessed at the end of study or when all patients have withdrawn, if this is sooner. For cohort B, ORR will apply to BOR from tumour assessments during IMM-101 + nivolumab treatment only. ORR and BOR will also be assessed for subgroups based on PD-L1 status (positive or negative/undetermined) in cohort A patients.

The primary safety endpoint of the study is the incidence, frequency and severity of AEs, serious adverse events (SAEs), treatment related AEs, immune-related AEs, Grade 3 and above AEs and AEs leading to IMM-101 discontinuation or study withdrawal experienced during treatment with IMM-101 + nivolumab for both cohorts.

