5.15 SAFETY EVALUATION

5.15.1 Adverse Events

AEs will be coded using the latest MedDRA dictionary version. The version used will be indicated in the data summaries and listings.

A treatment-emergent adverse event (TEAE) is defined as an AE that started on or after the start of the administration of IMM-101. If adverse event dates are incomplete and it is not clear whether the adverse event was treatment-emergent, it will be assumed to be treatment-emergent.

The relationship with each study treatment will be entered in to the eCRF for IMM-101, nivolumab and ipilimumab. A treatment-related TEAE is defined as a TEAE that is possibly, probably or definitely related to the study treatment. For each treatment, where the TEAE has a missing relationship it is assumed to be related to the treatment for analysis purposes.

A summary table will present the following:

- TEAEs (events and subjects).
- Serious TEAEs (events and subjects).
- Treatment-related TEAEs (relating to IMM-101 and/or nivolumab and/or ipilimumab) (events and subjects).
- Immune-related TEAEs (events and subjects).
- TEAEs with a Common Terminology Criteria for Adverse Events (CTCAE) Grade of 3 or above (events and subjects).
- TEAEs leading to discontinuation of IMM-101 (subjects only).

- TEAEs leading to withdrawal from study (subjects only).
- TEAEs leading to death (subjects only).
- TEAEs by CTCAE grade (1 to 5) (subjects only).
- TEAEs by severity (mild/moderate/severe/life threatening/death) (subjects only).
- TEAEs by relationship to study treatment and the pooled study treatment related category (subjects only).

In the above summaries, if a subject experienced more than one TEAE, the subject will be counted once using the most related event for the “by relationship to study treatment” and “related to IMM-101/nivolumab/ipilimumab” summaries, at the worst grade for the “by CTCAE grade” summary, and at the worst severity for the “by severity” summary.

A summary table will also be produced for Cohort B subjects only for AEs which occur at or after the start of infusion of ipilimumab. Any nivolumab related TEAEs occurring after the start of ipilimumab administration will be included. The summary will present the following:

- TEAEs (events and subjects).
- Serious TEAEs (events and subjects).
- Treatment-related TEAEs (relating to IMM-101 and/or ipilimumab) (events and subjects).
- Immune-related TEAEs (events and subjects).

The following tables will be presented:

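### Immune-related AEs are defined by the nivolumab SmPC list alone, so an immune-mediated event new to IMM-101 or the combination could be left out of the immune-related outputs

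*Protocol*

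**What the plan says.** Three protocol sections tie the term to the nivolumab product information. Section 5.2.1 includes in the primary safety endpoint "immune-related adverse events (as listed in the SmPC for nivolumab". Section 9.1 applies the same limit to the combination: "immune-related adverse events (as listed in the SmPC for nivolumab) for the combination of IMM-101 with nivolumab". Section 11.1.3 repeats it: "immune-related AEs (as listed in the SmPC for nivolumab), Grade 3 and above AEs". The exploratory summary after a switch uses the ipilimumab SmPC in the same way (Protocol 5.2.3 and 11.1.3).

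Elsewhere the term carries no definition. The synopsis has "treatment related AEs, immune-related AEs, Grade 3 and above AEs" and SAP 2.2.1 has "immune-related AEs, Grade 3 and above AEs and AEs leading to IMM-101 discontinuation or study withdrawal". SAP 5.15.1 plans a summary line, "Immune-related TEAEs (events and subjects", together with a table by SOC and PT and a separate listing. It does not say which events enter them. The SAP is based on Protocol Version 2, and its section 6 (changes from the protocol) leaves this definition alone.

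The treatment rules use a broader term. Protocol 7.3, like 7.2.1, begins one rule "In the event of any immune-mediated adverse reactions of ≥Grade 3 (severe), IMM-101 and nivolumab" and sets no SmPC restriction. Section 7.2.1 also foresees treatment delays for Grade 2 immune-related reactions. Section 9.1 says that the six-monthly safety reviews are held "with a particular focus on immune-related AEs".

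**The concern.** A primary objective is to describe the safety of adding an immune activator to nivolumab. Protocol 9.2.2 names IMM-101 as the only investigational product, yet the list that decides what counts as immune-related comes from the background drug. Such a list can show more of nivolumab's known reactions. It is a poor fit for a reaction that IMM-101 or the combination brings for the first time.

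Earlier experience gives little reassurance here. Protocol 3.4 reports two patients who had received IMM-101 with nivolumab, for only 12 weeks. In the same section the sponsor describes earlier IMM-101 data by an open category, events with an apparent immunological cause, which is wider than the list chosen for this trial.

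What is at stake is classification. An event that the Investigator manages as immune-mediated need not be one that the analysis labels immune-related, and the immune-related table is where a reader would look for it.

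**Working it through.** The plan gives no figure to reproduce. The endpoint is descriptive, and there is no sample size calculation, power or significance level (Protocol 11.2 and 11.3). The check is therefore a comparison of text, followed by simple arithmetic for scale.

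**Step 1. Is there another inclusion rule?** Protocol 9.2.3, 9.2.4 and 9.7 ask for grade and for causality to each drug. They describe neither an Investigator flag for immune-mediated events nor adjudication. The SmPC list is the only written rule for what is immune-related, and no SmPC version is fixed.

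**Step 2. Where would an unlisted immune-mediated event appear?** Two cases are traced through SAP 5.15.1:

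| Output | Grade 3+, IMM-101 permanently stopped | Grade 2, dose delay only |
|---|---|---|
| All TEAEs, overall and by SOC/PT | yes | yes |
| Treatment-related | if judged related | if judged related |
| Serious | if serious | if serious |
| Grade 3+ summary, SOC/PT table, listing | yes | no |
| IMM-101 discontinuation count and listing | yes | no |
| Full AE listing, with action taken per drug | yes | yes |
| Immune-related summary, SOC/PT table, listing | no | no |

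A Grade 3+ event with temporary withdrawal follows the first column but drops out of the discontinuation row. For the Grade 2 case, SAP 5.12 also summarises delays and their reasons, again without an immune-related label.

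**Step 3. Size.** Inputs: planned n = 18 in Cohort A and n = 8 in Cohort B (Protocol 11.2). The number of immune-related events is short by one for each unlisted event. The number of patients is short by one only if that patient has no listed immune event. In that case the understatement is 1/n:

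- Cohort A: 1/18 = 5.6 points. The table reads 0/18 (exact 95% CI 0 to 18.5%) in place of 1/18 (5.6%, 0.1 to 27.3%), if no other patient has a listed event.
- Cohort B: 1/8 = 12.5 points. The table reads 0/8 (0 to 36.9%) in place of 1/8 (12.5%, 0.3 to 52.7%), on the same condition.

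The intervals are Clopper-Pearson; for zero events the upper limit is 1 − 0.025^(1/n).

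**Step 4. How likely is at least one such event?** The documents give no rate. Purely as an assumption, take a true per-patient rate p of 2%, 5% or 10% and compute 1 − (1 − p)^n:

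- n = 18: 31%, 60%, 85%
- n = 8: 15%, 34%, 57%

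These figures only show how the answer depends on the assumed rate. They do not estimate it.

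**The case against.** The strongest reply is that nothing is lost. Grade 3+, treatment-related and discontinuation events are themselves components of the primary safety endpoint. An event that triggers the 7.2.1/7.3 rule is Grade 3 or above by definition, so it appears in the Grade 3+ outputs. With 26 planned patients, all listed with the action taken for each drug, an event that stopped both drugs would be seen. This stands. A reader might infer that the primary safety endpoint misses the event; the documents do not support that. The reply is weaker for a Grade 2 event that only delays dosing, as the table above shows.

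Second, the SmPC, the eCRF and the table shells are not available here. The list may be broad, and an immune-related flag may exist. A reader might infer that such events are certain to be missing from the table. The documents support only that the written definition would leave out any event not on the list; how many event types that covers cannot be checked.

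Third, 7.2.1 and 7.3 open by referring to the prescribing information, and they set a management trigger, not a rival endpoint definition. The sentence in 9.1 on six-monthly reviews covers all available safety data and carries no SmPC limit. Both points are fair. The contrast shows only that the protocol uses a wider concept when it manages patients than when it counts events.

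Fourth, a list tied to nivolumab suits the planned comparison with published nivolumab data (Protocol 4, SAP 2.1). That is a good reason to keep it as one row, but it does not make that row sufficient for a new combination.

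**Conclusion.** The point holds as a problem of classification. The only written rule for immune-related AEs is the nivolumab SmPC list (the ipilimumab SmPC for the post-switch summary). An immune-mediated event outside it would be left out of the immune-related summary, SOC/PT table and listing while remaining in the other AE outputs.

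The 5.6 and 12.5 points are what one omitted patient costs. They rest on planned enrolment and on that patient having no listed immune event. They are not an expected bias, because the frequency of unlisted events is unknown. A reader might scale the loss to the 11 and 5 patients named for the interim reviews. SAP sections 4 and 6 fix those sets for the response rate; interim safety takes everyone enrolled at the time, which may be more, so they are not the safety denominators.

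The change is worth making because it is cheap and serves a primary objective. No test or decision threshold depends on it.

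**What to change.** In Protocol 5.2.1, 9.1 and 11.1.3 and in SAP 5.15.1, define an immune-related TEAE as one that meets either condition:

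- it is listed in the nivolumab SmPC, with the version stated (the ipilimumab SmPC for the post-switch summary); or
- the Investigator recorded it as immune-mediated, including every event handled under the immune-mediated rule in 7.2.1/7.3.

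Show the SmPC-listed subset as a separate row, so that the comparison with published nivolumab data is kept. Bring the synopsis and SAP 2.2.1 into line with the same definition.

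The cost is one definition, one extra table row and, if the information is not already captured, one eCRF field. Events already recorded would need to be classified before database lock. The downside is that the broader row depends on Investigator judgement in an open-label study and may be slightly higher than the SmPC-listed row; showing both lets the reader see the difference. The treatment rules do not change.
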